**Data management and analysis**

Remote input of data (data into the electronic database will be entered by the participating physicians from the workplace). Data will be entered in depersonalized form.

The methods of descriptive statistics will be used for the whole population for all the indicators studied.

For those categories for which it is possible (for example, "high-density lipoprotein cholesterol"), the data will be reduced to time points "after 2 months"; "in 3 months"; "in 6 months"; "in 12 months", using the method move forward the last observation data (Last Observation Carried Forward, LOCF).

In addition, using descriptive statistics methods, all the studied indicators will be analyzed separately for the following populations:

- population in which a set of preventive measures was carried out (in-

depth medical advice to patients about taking therapy, sms reminders about the need to follow the doctor's prescription)

- population in which a set of preventive measures was not carried out.

Using the methods of comparative statistics, the following variables will be compared:

- Change in the lipid spectrum of the blood during the study period:  
(A) in the whole population  
(B) in a population in which a set of preventive measures was carried out (in-depth medical advice to patients about taking therapy, sms-reminders about the need to follow the doctor's prescription)  
(C) in a population in which a set of preventive measures was not carried out.

In addition, using the methods of comparative statistics, the following indicators will be compared:

- reasons for withdrawal of therapy
- duration of statin therapy: between groups; for each trade name
- Percentage of patients who continued to receive statins at the end of the main part of the program (6 months): between groups; for each trade name
- Percentage of people who continued to receive statins at the end of the 6-month continuation of the main part of the program (12 months): between groups; for each trade name
- results of Moriski-Green test
- blood pressure
- smoking status
- change in body mass index
- development of one of the following conditions (occurrence of the following diseases, development of the following events) during the study period:  
(A) myocardial infarction  
(B) stroke  
(C) transient ischemic attack  
(D) ischemic heart disease  
(E) heart failure  
(F) atherosclerosis of brachiocephalic arteries  
(G) atherosclerotic disease of peripheral arteries  

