(H) hospitalization  
(I) call an ambulance  
(K) revascularization  
(K) death,

in a population in which a set of preventive measures was carried out (in-depth medical advice to patients about the admission of therapy, sms-reminders about the need to follow the doctor's prescription), and in a population in which a set of preventive measures was not carried out.

At the end of the study, a final report will be prepared in Russian.

**General description of the study** 6 centers of medical prevention (MSC), located in different regions of Russian Federation will take part in this project, in cooperation with other medical and preventive institutions.

During the **first** phase of the project (screening 1) is expected to be screened in the existing health care institutions of primary health care databases (patients, healthy individuals) and identify individuals;

- (a) not currently suffering from cardiovascular disease (diseases), which are exclusion criteria for this scientific program,
- (b) do not have the history of conditions (diseases), which are exclusion criteria in this scientific program,
- (c) not receiving statin for the prevention of cardiovascular disease,
- (d) having risk factors for cardiovascular disease.

Sufficient number of subjects should be screened in each center to include 2,000 patients who meet the inclusion and exclusion criteria in the project.

During the **second** phase of the project (screening 2) subjects will be invited to the study centre in medical prevention and treatment-and-prophylactic institutions (MPI), or to physician to confirm that subject:

- (a) does not currently suffer from cardiovascular disease (diseases), which are exclusion criteria for this scientific program,
- (b) does not have a history of conditions (diseases), which are exclusion criteria for this scientific program,
- (c) does not receive statins for the prevention of cardiovascular diseases,
- (d) has risk factors for cardiovascular disease,
- (e) has reasonable indications for determining the lipid spectrum.

During the **third** phase of the project (screening 3) subjects who were selected during the second phase, will be determined lipid profile by express test.

Persons with lipid metabolism disorders, which are indications for prescribing vital and essential statins for the prevention of cardiovascular diseases, are prescribed statins in accordance with standard practice of medical institution.

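### Minor: the lipid comparison lists change in the whole population and in each arm without naming the contrast; state that the randomised arms are compared, adjusted for baseline

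*Protocol*

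**What the plan says.** All statements here are in the protocol.

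- **Description.** Data management and analysis first provides descriptive statistics for the whole population. It then adds that "all the studied indicators will be analyzed separately for the following populations", meaning those with and those without the set of preventive measures.
- **Lipid line.** Under comparative statistics it lists "Change in the lipid spectrum of the blood during the study period", with item "A) in the whole population", item B for those given the measures and item C for those not given them. What is to be set against what is not stated.
- **Second list.** A further list of comparisons names its contrast. One entry is "duration of statin therapy: between groups; for each trade name", and statin persistence at 6 and 12 months is worded the same way. The list closes by placing the population with the measures beside the other: "and in a population in which a set of preventive measures was not carried out".
- **Time points.** For lipids, "the data will be reduced to time points" at about 2, 3, 6 and 12 months, by last observation carried forward (LOCF).
- **Order of events.** In General description of the study, third phase, subjects "will be determined lipid profile by express test", and those with an indication "are prescribed statins in accordance with standard practice of medical institution". Consent and inclusion follow the prescription. Randomisation 1:1 comes in the fourth phase.
- **Reminders.** SMS and calls, which also cover the follow-up visit, go only to the in-depth consultation arm.

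**The concern.** Each arm is described separately just above, so the lipid line under comparative statistics should mean a test. Item A contains B and C, and change over time is the only thing that can be tested in A alone. If B and C are read in parallel with A, the result is three before-after tests and no comparison of the randomised arms.

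Both arms start a statin. Before-after change in either arm therefore mainly reflects the statin, plus some regression to the mean in those selected on LDL. Significant falls would be expected in both arms even if the consultation and reminders did nothing. The section on potential consequences hopes to show the benefit of the measures. Lipid results could support that only through the randomised contrast. Lipids are also a stated focus of the project (Study condition).

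**Working it through.** **Plan's own figure.** 6 centres × 2,000 = 12,000, which reproduces the target number. At 1:1 this is 6,000 per arm. The protocol gives no SD, effect size, alpha or power, so there is no further figure to reproduce.

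**1. Which contrasts can A, B and C give?** At 1:1, mean(A) = [mean(B) + mean(C)]/2, so A − B = (C − B)/2. Setting A against B or C adds nothing to B versus C. Two readings remain: change over time within each population, or B versus C.

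**2. What does before-after change show if the measures do nothing?** Assumptions, not in the protocol: two-sided alpha 0.05, normal approximation, the same true fall *s* in both arms (in SDs of change), *n* values per arm. The probability that the test within one arm is significant is Φ(s√n − 1.96) + Φ(−s√n − 1.96). With n = 6,000, √n = 77.46:

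| Shared fall (SD) | s√n | Before-after significant | B versus C significant |
|---|---|---|---|
| 0.02 | 1.55 | 0.34 | 0.05 |
| 0.05 | 3.87 | 0.97 | 0.05 |
| 0.10 | 7.75 | over 0.999 | 0.05 |

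This does not depend on complete retesting. Both arms are significant together in 95% of such trials when s = (1.96 + 1.954)/√n = 3.914/√n, where 1.954 is the normal quantile of √0.95. That is 0.051 SD at n = 6,000 and 0.160 SD at n = 600 (10% retested).

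**3. Why adjust for baseline?** Let ρ be the correlation of baseline with follow-up, and take equal variance σ² at both times. The variance per patient is 2σ²(1 − ρ) for raw change and σ²(1 − ρ²) after baseline adjustment. The ratio of adjusted to raw is (1 + ρ)/2, which is below 1 for any ρ below 1. The baseline value is already measured at screening, so this gain is free. Comparing raw change between randomised arms would still be valid.

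**4. What does LOCF add?** The protocol does not say whether a baseline value may be carried forward. If it were, a patient never retested would count as zero change. With shares m_B and m_C retested and the same true mean fall D in both arms, the apparent difference would be (m_B − m_C) × D. Visit reminders go to one arm only, so m_B and m_C may differ.

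**The case against.** The strongest reply is that the lipid line already means B versus C. Its lead-in announces a comparison, both arms are listed, and description by arm has been dealt with above. The second list is introduced as a continuation of the same exercise, and its closing clause uses nearly the same wording where it plainly serves the two arms. The between-groups phrase appears only where it must be told apart from a comparison by trade name. Blood pressure, body mass index and the Morisky-Green test lack it too, yet the closing clause covers them. The text also reads like a translation, so fine inference from phrasing is weak. Item A may simply be the overall change shown beside the arm comparison. Finally, an SAP may settle the contrast.

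Most of this stands. B versus C is a fair reading, and the wording alone comes close to detail that an SAP would supply. What remains is that the closing clause is attached to the second list and not to the lipid line, so an analyst following the text could run three before-after tests.

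A reader might go further and infer that the protocol omits a randomised lipid comparison, or that it means to offer falls within arms as proof that the measures work. The documents do not support either. The contrast is left open, not excluded. Objective 6 defines the effect of the measures as an effect on compliance, and the sentence on their advantages does not mention lipids.

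**Conclusion.** This is a minor point and a worthwhile improvement. The lipid contrast is ambiguous, and B versus C is the only one of the listed contrasts that bears on the randomised consultation and reminders. Before-after change in A, B and C remains a fair description for objective 7, and of the wider 3P project, in which everyone starts a statin.

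The weight is limited. No primary endpoint is named, lipids are one of many outcomes, and statin duration and persistence have explicit between-group comparisons. The order of events is taken from the protocol, and B and C are taken to be the two randomised arms. The probabilities above rest on an assumed common fall and assumed numbers retested, and only show the direction of the problem. Whether the trial has enough retested patients to detect a lipid difference is a separate question and is not claimed here.

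**What to change.** Amend the lipid line in Data management and analysis along these lines:

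- Total cholesterol, LDL, HDL and triglycerides at 6 months, and at 12 months in extension sites, are compared between the two randomised arms (B versus C), adjusted for the patient's baseline value and site.
- Changes over time in A, B and C are reported descriptively, with no inference about the consultation and reminders.
- The number of values actually measured at each time point is reported per arm, and a carried-forward baseline value does not count as a follow-up result.

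The cost is a few lines of wording. Baseline lipids come from the screening express test, and 6- and 12-month values are already planned, so no new data are needed. The drawback is that follow-up lipids depend on usual-practice visits with no fixed dates. The number evaluable, and so the precision, cannot be known in advance and may differ between arms.

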### **Objectives of the project**

1. To make physicians (internists, cardiologists, medical specialists working in preventive facilities) familiar with current approaches to assessment of cardiovascular risks and their management through timely administration of corresponding treatments, by organization of training activities (web conferences, meetings, round table discussions).
2. To inform physicians, especially those in primary care, on the importance of a thorough assessment of cardiovascular risks and timely administration of therapy.
3. To analyze databases currently effective in medical institutions (those on healthy subjects and patients) in order to identify subjects with cardiovascular risk factors.
4. To assess blood lipids in subjects with suspected high cardiovascular risk.
5. To perform in-depth medical consultations of subjects on the importance of primary cardiovascular prophylaxis, including by means of preventive statin treatment (with the information on original drugs and generics, social programs by manufacturers implemented in pharmacies).
6. To assess efficacy of the combination of preventive activities (in-depth medical consultation of patients on their treatment; sms reminders on the necessity to comply with their doctor's prescriptions) on patients' compliance to treatment.
7. To follow changes in cardiovascular risk factors with associated assessment of patients' compliance to medical recommendations.

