**Potential medical, social and economic consequences of the project**

The results of the project (medical statistical and pharmaco-epidemiological) will be presented to the Russian medical community and healthcare institutions in order to:

- (a) draw attention to the problem of primary prevention of cardiovascular diseases,
- (b) based on the analysis of the results of the study help healthcare professionals and healthcare providers to choose the right line for treatment people with high cardiovascular risks, including timely administration of statins,
- (c) demonstrate the advantages of complex preventive measures (profound consultation about necessity of maintenance the doctor's recommendations; sms reminders about the need to follow the doctor's prescription),

having the aim of reducing the number of cardiovascular diseases in Russian Federation.

In order to promote the development of modern approaches to the prevention of cardiovascular diseases, to demonstrate to a wide range of doctors the benefits of timely prescription of statins for primary prevention of cardiovascular diseases, during the project it is planned to hold meetings, conferences, roundtables on the prevention of cardiovascular diseases with the aim of discussing the progress of scientific research in Russia and abroad, as well as the participation of physicians in the work of international congresses and conferences with the purpose of increasing their own knowledge and further transfer of this knowledge to Russian specialists.

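### Nineteen between-arm comparisons are listed with no primary outcome, and none of the four compliance measures is singled out to decide the efficacy question

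*Protocol*

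**What the plan says.** Objective 6 of the protocol (Objectives of the project) is "To assess efficacy of the combination of preventive activities" with respect to compliance with treatment. The section on potential consequences expects the results to "demonstrate the advantages of complex preventive measures". The General description of the study randomises subjects 1:1 to in-depth consultation with reminders or to standard practice. The target is 12,000 patients, 2,000 in each of six centres.

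The Data management and analysis section first plans comparative statistics for lipid change, in the whole population and in each of the two groups. It then states that, in addition, "using the methods of comparative statistics, the following indicators will be compared", and the list ends by naming the populations with and without the preventive measures. The list contains:

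- why treatment was stopped
- how long statins were taken, by trade name and by arm
- "Percentage of patients who continued to receive statins at the end of the main part of the program (6 months): between groups", and the same at 12 months
- "results of Moriski-Green test"
- blood pressure, smoking status and change in body mass index
- eleven clinical event types, from myocardial infarction to death.

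No item is called primary, no order of importance is given, and no deciding time point is set.

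**The concern.** A randomised comparison that is meant to establish efficacy needs one outcome, fixed in advance, that decides the question. This protocol names an intention to show advantages and a long list of comparisons, but does not connect the two. Objective 6 narrows the question to compliance, yet compliance appears as Morisky-Green result, duration of statin therapy, continuation at 6 months and continuation at 12 months. These could disagree, and nothing says which would prevail.

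The choice of deciding outcome is a design commitment that belongs in the protocol. It differs from the details of testing, which may properly sit in a statistical analysis plan. Without it, the claim about the intervention has no defined error rate, and readers of the final report cannot tell whether the emphasised result was the one intended.

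**Working it through.** **Stated figure.** The protocol gives no significance level, power or error rate, and 12,000 is simply 6 × 2,000. There is no figure of the plan's own to reproduce.

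**Count of comparisons** (Data management and analysis)

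- Indicators: reasons for withdrawal, duration, 6-month continuation, 12-month continuation, Morisky-Green, blood pressure, smoking, body mass index = 8.
- Events: myocardial infarction, stroke, transient ischaemic attack, ischaemic heart disease, heart failure, brachiocephalic atherosclerosis, peripheral artery disease, hospitalisation, ambulance call, revascularisation, death = 11.
- Total 8 + 11 = 19.
- Systolic and diastolic pressure tested separately (Data to be collected records both): 20.
- Four lipids also compared between arms: 20 + 4 = 24.

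Trade-name and repeated time-point analyses are not counted, because the protocol does not say how many there are or whether each is an arm comparison.

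**Assumption.** Each comparison is tested at two-sided 5%, so 2.5% in the favourable direction.

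**Independent tests.** Chance of at least one false positive among m tests, with no true effect:

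- Either direction, 1 − 0.95^m: m = 19 gives 62.3%; m = 20 gives 64.2%; m = 24 gives 70.8%.
- Favouring the intervention, 1 − 0.975^m: m = 19 gives 38.2%; m = 20 gives 39.7%; m = 24 gives 45.5%.

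**Correlated tests.** The protocol gives no correlations, so a range is shown. Normal test statistics with a common correlation were simulated (200,000 replicates):

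| Correlation | Either direction, 20 tests | Either direction, 24 tests | Favourable, 20 tests | Favourable, 24 tests |
|---|---|---|---|---|
| 0.3 | 54% | 60% | 28% | 31% |
| 0.5 | 42% | 46% | 21% | 23% |
| 0.7 | 29% | 31% | 15% | 16% |

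**Compliance measures only** (m = 4, independent)

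- Either direction: 1 − 0.95^4 = 18.5%.
- Favourable: 1 − 0.975^4 = 9.6%.

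Both are ceilings, since duration, continuation and Morisky-Green overlap.

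**Benchmark.** One primary comparison at two-sided 5% carries 5% in either direction and 2.5% in the favourable direction.

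**The case against.** The strongest reply is that the efficacy objective is narrower than the list. Objective 6 concerns compliance, the project title also names it, and changes in risk factors fall under objective 7, which only sets out to follow them. On that reading about four measures bear on efficacy, and the relevant ceiling is 19% rather than 62-71%. This stands as a limit on the size. It does not remove the point, because none of the four is singled out and the aim of showing advantages is not confined to compliance.

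A reader might infer that any one significant item would be declared proof of benefit, with a 64-71% chance of a false claim. The documents do not support that. No sentence says that a single significant item establishes benefit. The 64-71% range needs 20 to 24 tests where 19 are listed, an unstated 5% level and independence, and it counts errors against the intervention as well as for it. The lipid item is listed for the whole population and each group, without an explicit arm contrast.

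It may also be said that a statistical analysis plan could settle this. That holds for significance level, test order and stratification. It does not hold for which outcome decides a randomised question. Nor does the protocol's description of the study as non-interventional make these analyses descriptive: the same section separates descriptive from comparative methods, and this list is under the latter.

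Finally, the choice of month 6 over month 12, or of continuation over Morisky-Green, is a judgement that the documents do not make. That is accepted, and the fix offers it as an example.

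**Conclusion.** The concern holds in this form: 19 listed between-arm comparisons (20 to 24 on wider readings), no primary outcome, and four unranked measures of the one construct that the efficacy objective names.

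All error rates rest on an assumed two-sided 5% per test. The either-direction figure of 62-71% is an upper limit that requires independence, which is implausible for overlapping adherence measures and related cardiovascular events. For a false claim of benefit, the relevant figures are about 40-46% if independent and 28-31% at correlation 0.3 (20 to 24 tests). If only the compliance measures count, the ceiling is 10% favourable and 19% in either direction. Even this narrowest ceiling is almost four times what a single primary comparison would carry. The collected data remain usable; the gap is in what the main claim will rest on, and it should be closed before the arms are compared.

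**What to change.** In Data management and analysis, name one already listed compliance measure at one time point as the primary between-arm comparison, in all randomised patients, at two-sided 5%. Statin continuation at month 6 is a natural candidate: all sites take part to month 6, while the extension is limited to sites that consent to it (Methodology of the study).

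Three details must go with it:

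- A window defining the month-6 assessment, because the Time points of assessments section sets no concrete visit dates.
- A rule for randomised patients with no assessment in that window.
- A statement that the choice was made before any arm-level results were seen. Version 3 is dated March 30, 2018 and first patient in was planned for May 1, 2017, so on schedule early patients had already reached six months.

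Report all other comparisons as secondary or exploratory estimates with 95% confidence intervals that do not on their own support a claim of efficacy.

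The cost is a short protocol amendment and the loss of confirmatory status for the other comparisons; none is deleted. Precision should not be an obstacle. With 6,000 per arm, 80% power and complete outcomes, the detectable difference is 2.80 × √(2p(1 − p)/6000), which is 2.3 percentage points at p = 0.70 and 2.6 at p = 0.50. Power, completeness and the 50-70% continuation range are assumptions, not protocol figures.
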